## CLINICAL STUDY PROTOCOL SUMMARY

**Title of Study:** Validation of the Concept of COPD Control In Clinical Practice

**Protocol version:** 1.0

**Study Number:** REG-RES1503

**Chief Investigator:** [name]

**Clinical Research Organisation:** Respiratory Effectiveness Group

**Part study funder:** REG and Novartis

**Name of Active Ingredients:** NA

**Name of Investigational Product:** NA

**Phase of Clinical Development:** 4

**Number of Investigational Centres Planned:** approximately 10 Centres

**Country of the study:** International – Spain, France, UK, Ireland, Canada

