**General Design and Methodology:**

This is a 21-month pragmatic non-interventional trial comprising one baseline assessment and 4 follow-up visits.

**Objectives:** The primary aims of the study will be to evaluate the:

- Levels of COPD control (vs poor COPD control) in an international cohort of routine care COPD patients, and
- The clinical implications of control status.

Secondary objectives of the study are to:

- Compare the utility of the COPD Control (as defined) as a tool to identify COPD impact and stability with the CAT and CCQ;
- Evaluate the role of “adequate” (i.e. guideline-recommended) treatment prescribing on COPD control.
- Identify demographic and clinical characteristics associated with COPD control
- Evaluate the cost-utility of patients with controlled (as compared to poorly controlled) COPD.

**Number of Patients Planned:** 328

**Study Population:** It is planned to enrol approximately 328 patients older than 40 years with a diagnosis of COPD. The diagnosis of COPD will be based on a post-bronchodilator FEV1/FVC<0.7 in patients smokers or smokers of at least 10 pack-years, in accordance with the Global Initiative for Obstructive Lung Disease (GOLD).

**Length of the Study:** Length of the study will be approximately 21 months from baseline screening to final patient follow-up.

**End of the Study:** Last patient’s last visit.

**Inclusion Criteria:** Patients may be included in the study if they meet all of the following criteria:

- Spirometry-defined COPD (i.e. post-bronchodilator FEV1/FVC<0.7)
- Age ≥40 years
- Smokers or ex-smokers of at least 10 pack-years
- In stable state (as judged by the investigator) at point of recruitment

**Exclusion Criteria:** Patients will be excluded from participating in this study if they meet any of the following criteria:

- Have any concomitant chronic respiratory condition other than asthma or bronchiectasis (e.g. cystic fibrosis, lung fibrosis)
- Have severe comorbidity with a life expectancy shorter than 2 years
- Are unable to understand the instructions of the study or to fill the questionnaires
- Are unwilling to sign the informed consent
- Are participating in another clinical study or clinical trial

**Investigational Product:** NA (non-interventional study)

**Placebo:** NA (non-interventional study)

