## Definition of COPD Control

Control of COPD is defined as a composite of low disease impact, adapted to the patients' level of COPD severity, and clinical stability over time.

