## 2. STUDY OBJECTIVES AND RATIONALE

### 2.1. Hypothesis

Control in COPD is a new conceptual dimension requiring demonstration of both low impact and clinical stability. The developers of the concept hypothesize that a status of control in COPD will be associated with better clinical outcomes (reduced frequency of exacerbations and mortality and improved health-related quality of life); reduced rate of decline in lung function and/or BODE/BODEx and reduced direct COPD-related healthcare costs.

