#### 4.4.2. Visits 0–3: Baseline and follow-up assessment

In baseline visit (3 months after screening visit) patients will be included in one of the study groups (controlled patients or uncontrolled patients) according definitions. The following data will be collected at the time of each follow-up visit in order to assess disease stability between follow-up visits and disease control at time of each visit.

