#### **9.3.4. Analysis of secondary outcomes**

Secondary outcomes (EQ5, CCQ, changes in lung function, BODE index) will be analyzed using analysis of covariance (ANCOVA), once assumptions for the convenience of this analysis are confirmed, with baseline values and potential confounding factors as covariates and study group as independent variable (Miller, G. A., & Chapman, J. P. 2001). After, Least square (LS) mean  $\pm$  standard error (SE) will be calculated for variables involving each outcome.

Baseline differences between study groups (controlled and uncontrolled COPD patients) will be performed using the Chi-square test (exact Fisher test with observed frequencies  $< 5$ ) for categorical variables whereas continuous variables were tested using *t* test (U-Mann Whitney test if the variables were not normally distributed). A stepwise multivariate logistic regression model to predict control in COPD patients will be performed. All variables explored in the univariate analyses will be considered in the multivariate model as covariates. A conservative significance threshold of 0.01 was used to determine the qualification of data for entry into or deletion from the model.

Finally, an analysis will be performed to evaluate the cost-utility of patients with controlled (as compared to poorly controlled) COPD using analysis of covariance. Data will be collected from the economic department of each collaborating center.

All tests were two-tailed, and significance was set at 5%. All analyses will be carried out using SPSS version 20, SAS version 9.3 and Microsoft Office EXCEL 2007.

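### The promised cost-utility of controlled versus poorly controlled COPD cannot come from this analysis, which supports only separate cost and EQ5-D differences by control status

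*Protocol*

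**What the plan says.** The protocol summary lists as a secondary objective: "Evaluate the cost-utility of patients with controlled (as compared to poorly controlled) COPD". Section 9.3.4 fixes the method: "an analysis will be performed to evaluate the cost-utility of patients with controlled (as compared to poorly controlled) COPD using analysis of covariance". It adds the source: "Data will be collected from the economic department of each collaborating center". Section 2.1 gives the expected direction, "reduced direct COPD-related healthcare costs".

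The groups come from a classification. Under Definition of COPD Control, "Control of COPD is defined as a composite of low disease impact", adapted to severity and combined with clinical stability. Section 4.4.2 says that at the baseline visit "patients will be included in one of the study groups (controlled patients or uncontrolled patients) according definitions". Section 5 provides for usual care throughout, and the summary calls the study non-interventional.

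The summary gives the countries as "International – Spain, France, UK, Ireland, Canada" and the number of sites as "approximately 10 Centres".

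**The concern.** A cost-utility analysis sets the extra cost of one course of action against its extra utility, usually in QALYs. Here nobody is offered a course of action. Patients are labelled by their symptoms or CAT/CCQ scores, the absence of recent exacerbations and the stability of their scores. A later difference in cost or EQ5-D describes patients who were already better or worse off at classification. It does not show what it would cost to move a patient from one group to the other, or what would be gained.

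What is at stake is interpretation. Section 2.3 says that the secondary objectives are meant to help guide treatment decisions and to find patients in whom cost efficiencies can be achieved. A result labelled cost-utility could then be read as evidence that a strategy aimed at control is good value, which this design does not test.

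A smaller concern is the cost contrast itself. Cost data come from centres in five countries with three currencies, so differences in price level could enter the comparison if the data were pooled at local prices.

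**Working it through.** The protocol gives no figure for this analysis, so there is none to reproduce. The main point is checked by setting the sections side by side, and the price point by arithmetic.

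**1. Objective against design and data**

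- Options compared: none. Control is a state (Definition of COPD Control), assigned by classification (section 4.4.2) under usual care (section 5).
- Joint measure: none. Section 9.3.4 names ANCOVA but no QALY, incremental ratio or net benefit. ANCOVA on cost gives an adjusted cost difference, and ANCOVA on EQ5-D an adjusted EQ5-D difference.
- Utility data: section 4.4.1.3 has EQ5-D evaluated at inclusion so that change can be assessed at follow-up, and section 9.3.4 lists EQ5 among the secondary outcomes. EQ5-D is absent from Tables 4, 5 and 7 and from the variable lists in sections 9.3.1 and 9.3.2.
- Cost data: sections 9.3.1 and 9.3.2 list the cost of COPD and of other medications. No cost item is listed for hospital, emergency or physician contacts, although section 2.1 hypothesises lower direct COPD healthcare costs.
- Outcome list: none of the six secondary outcomes in section 4.3.2 is a cost or a utility.

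**2. Price level as a confounder (illustration)**

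From the protocol: five countries (summary), 55% controlled and 285 evaluable patients (section 4.5), two-sided 5% (section 9.3.4). Assumed, because the documents do not say: equal-sized countries; the same resource use in both groups; local prices rising evenly from 1 to r; and the share controlled, c, moving evenly across 55% ± d.

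Mean cost, controlled = Σ(price × c) / Σc. Mean cost, uncontrolled = Σ(price × (1 − c)) / Σ(1 − c).

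Worked case, r = 1.5 and d = 10 points, with control commoner where prices are lower. Prices are 1, 1.125, 1.25, 1.375, 1.5 and c is 0.65, 0.60, 0.55, 0.50, 0.45.

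- Controlled: 3.375 / 2.75 = 1.227
- Uncontrolled: 2.875 / 2.25 = 1.278
- Ratio 0.960, an apparent saving of 4.0%. With c reversed, 1.273 / 1.222 = 1.041, an apparent excess of 4.1%.

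Apparent cost difference for controlled patients with identical resource use (control commoner in cheaper countries / in dearer countries):

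| r | ±5 points | ±10 | ±15 | ±20 |
|---|---|---|---|---|
| 1.25 | −1.1% / +1.1% | −2.2% / +2.3% | −3.3% / +3.4% | −4.4% / +4.6% |
| 1.5 | −2.0% / +2.0% | −4.0% / +4.1% | −5.9% / +6.3% | −7.7% / +8.5% |
| 2.0 | −3.3% / +3.4% | −6.5% / +7.0% | −9.6% / +10.7% | −12.5% / +14.5% |

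With equal prices or equal shares controlled, the difference is zero.

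**3. Effect on the test**

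Simulation with 285 patients, gamma costs with coefficient of variation 1 (assumed), 4,000 runs and a linear model on cost, with control commoner in the cheaper countries. Rejection rate at nominal 5%:

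| r, d | No country term | Country in model |
|---|---|---|
| 1.5, ±10 | 6.2% | 5.2% |
| 1.5, ±20 | 9.2% | 4.7% |
| 2.0, ±10 | 8.2% | 5.5% |
| 2.0, ±20 | 18.5% | 5.3% |

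One common price set gives 5.3% without a country term. The simulated model has no baseline cost covariate. Including one would probably absorb part of the price level, so the first column is better read as an upper guide.

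**The case against.** The strongest defence is that this is loose labelling in a validation study. Groups are fixed at Visit 0 and outcomes are observed later. EQ5-D is not part of the control definition, and lower later cost is a stated hypothesis, so testing whether control predicts cost and utility is legitimate. This stands, and it is why the proposal keeps both comparisons and changes only what they are called and what may be concluded.

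Four stronger readings are tempting, and the documents do not support them.

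- A reader might infer that control is bound to come out as both cheaper and better. The protocol lists medication costs for all patients at baseline and follow-up, and controlled patients could be on dearer maintenance treatment. Nothing in the documents settles the direction of total cost.
- A reader might infer that ANCOVA can never give a joint result. A linear model on net monetary benefit would do so. The fair statement is that the protocol names no such quantity.
- A reader might infer that a saving will be manufactured by prices. Section 9.3.4 says only where the data come from. It does not say that local prices will be pooled unadjusted, and the data could be resource counts. A price set and a country covariate are commonly left to a later plan, so their absence is not an error in itself.
- A reader might infer that ANCOVA must give way to a gamma or bootstrap method. That is a preference about skewed costs and not a fault in the protocol.

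It can also be said that the stakes are modest, since the objective is secondary and section 4.3.2 carries no cost outcome. That is true, but a result under this label could still be published as a cost-effectiveness finding.

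**Conclusion.** The concern holds for the objective and its analysis. As written, the protocol promises a cost-utility result from a comparison of two health states, with no strategy compared, no joint measure named, and EQ5-D missing from the data lists that should support it. The study can deliver an adjusted difference in cost and, separately, in EQ5-D by baseline control status. This rests on the protocol's own text and on no numerical assumption, and a later analysis plan could not supply the missing comparator.

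The price point is a safeguard only. It needs both prices and the share controlled to differ by country, and costs to be analysed at local prices without adjustment. Under the assumed price ratios of 1.25 to 2.0 and shares varying by ±5 to ±20 points, the bias is an apparent saving of 1.1% to 12.5% or an apparent excess of 1.1% to 14.5%. In a middling case (1.5, ±10) the false-positive rate is 6.2%, little above nominal. The actual size cannot be derived from the documents.

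**What to change.** - In the summary objective and in section 9.3.4, replace the cost-utility wording with the difference in direct COPD cost and, separately, in EQ5-D by baseline control status. State that no cost-utility or cost-effectiveness claim will be made.
- Add EQ5-D to Tables 4, 5 and 7 and to the variable lists in sections 9.3.1 and 9.3.2, so that they agree with sections 4.4.1.3 and 9.3.4.
- Value resource use with one common price set or currency conversion, and include country as a covariate in the cost model. Five countries use four degrees of freedom, which 285 evaluable patients can bear.

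The cost is two reworded sentences, several list entries and one price table. EQ5-D has to be confirmed at the follow-up visits, which adds a questionnaire there if it was not already intended. Resource use has to be counted, but hospitalisations, emergency attendances and unscheduled COPD visits are already needed for the composite endpoint in section 4.3.1. The term cost-utility is given up. Keeping it would require a defined strategy whose incremental cost and QALYs can be estimated, which is a different comparison.

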#### 9.4. Missing data

The per-protocol will not account for missing data as missing data will be seen as a protocol violation and therefore a patient with missing data will be excluded from this population.

The Intent-to-Treat population (ITT) will have missing values imputed as follows:  
Any missing data will be assessed and attempts made to ensure that there are no underlying reasons for the data not being collected. i.e. that the data are missing at random.

## 10. ELECTRONIC CASE REPORT FORM & STUDY DATASET

### 10.1. Data collection

A clinical data management system (CDMS) will be used to hold data collected during the study. Data will be incorporated into the system from the eCRF. The CDMS will be fully validated to ensure that it meets the scientific, regulatory, and logistical requirements of the study before it is used to capture study data. Before using the CDMS, all users will receive training on the system and any study-specific training. After they are trained, users will be provided with individual system access rights.

Data will be collected at the investigational centres by appropriately designated and trained personnel and CRFs must be completed for each patient screened who provided informed consent/assent according to the data source. Patient identity should not be discernible from the data provided on the CRF. Data will be reviewed for consistency by Data Management using both automated logical checks and manual review. All data collected will be approved by each investigator at each investigational centre. This approval acknowledges the investigator's review and acceptance of the data as being complete and accurate.

### 10.1. Electronic case report form (eCRF)

An eCRF will be designed for the purposes of recording study information provided by the patient during study visits. Features of the eCRF will include:

- Password protected, with access limited to staff essential for entering or verifying data.
- Identification of patients by unique patient and practice identifiers to maintain patient confidentiality.
- Ensure that each time the patient record is accessed by a Researcher, Investigator or Monitor, the access will be logged.
- Data management strategies to minimise missing data and incorrect data entry.

Data captured into the eCRF will be directly incorporated into the database system.

### 10.2. Data quality control

Data Management is responsible for the accuracy, quality, completeness, and internal consistency of the data from this study. Data handling, including data quality assurance, will comply with international regulatory guidelines, including ICH GCP

guidelines. Data management and control processes specific to this study, along with all steps and actions taken regarding data management and data quality assurance, will be described in a Data Management plan.

Data captured will be processed and reviewed for completeness, consistency, and the presence of mandatory values. Applicable terms will be coded according to the coding conventions for this study. Logical checks will be implemented to ensure data quality and accuracy. Any necessary changes will be made in the clinical database, and data review and validation procedures will be repeated as needed.

### **10.3. Data queries**

Data queries will be raised by the data management team and the trial monitor to be resolved by the Investigator team.

## **11. QUALITY CONTROL AND QUALITY ASSURANCE**

### **11.1. Protocol amendments and protocol deviations**

#### **11.1.1. Protocol amendments**

No changes from the final protocol will be initiated without prior written approval and favourable opinion of a written amendment by the Research Ethics Committee (REC), except when necessary to address immediate safety concerns to the patients or when the change involves only logistics or administration.

Each Principal Investigator and the sponsor will sign the protocol amendment.

#### **11.1.2. Protocol deviations**

Any significant deviation from the protocol will be considered a protocol violation. Protocol violations include non-adherence on the part of the patient, the investigator, or the sponsor to protocol-specific inclusion/exclusion criteria, primary objective variable criteria, or GCP guidelines; noncompliance to study drug administration; use of prohibited medications; or any other deviations that may have an impact on the processes put in place for the care and safety of the patients.

When a protocol violation is reported, the sponsor will determine whether to discontinue the patient(s) affected by the violation from the study or permit the patient(s) to continue in the study, with documented approval from the medical representative. The decision will be based on ensuring patient safety and preserving the integrity of the study.

Deviations from the inclusion/exclusion criteria of the protocol are not prospectively granted by the sponsor. If investigational centre personnel learn that a patient who did not meet protocol eligibility criteria was entered into the study, they must immediately inform the sponsor of the protocol violation. If such a patient has already completed the study or has withdrawn early, no action will be taken but the violation will be recorded.

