## 9. STATISTICAL ANALYSIS

### 9.1. General

Intention-to-treat and per-protocol analyses will be undertaken. For the Intention-to-treat analysis, all patients entered into the study will be included in the analysis. For the per-protocol analysis, all patients entered who complete the study as per protocol (defined as attending baseline and all follow-up visits irrespective) will be included.

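### Sections 11.1.2 and 6.2 let a protocol violation or deviation end a patient's outcome follow-up by discretionary decision, in a cohort with no study treatment to stop

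*Protocol*

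**What the plan says.** Section 11.1.2 sets a threshold: "Any significant deviation from the protocol will be considered a protocol violation". Its examples include "noncompliance to study drug administration; use of prohibited medications". After a report, "the sponsor will determine whether to discontinue the patient(s) affected by the violation from the study". Alternatively, the sponsor may let the patient carry on, provided that a medical representative has approved this in writing. The stated criterion is: "The decision will be based on ensuring patient safety and preserving the integrity of the study".

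Section 6.2 separately allows the investigator to withdraw a patient for a protocol deviation. It asks for observations up to the time of withdrawal and a complete final evaluation at that point. It also refers to a study drug when describing the follow-up of adverse events.

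The summary describes the design: "This is a 21-month pragmatic non-interventional trial comprising one baseline assessment and 4 follow-up visits". It gives the investigational product and blinding as not applicable. Section 5 says that patients receive usual care and that the research team does not contact them outside the study visits.

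On analysis sets, section 9.1 states: "For the Intention-to-treat analysis, all patients entered into the study will be included in the analysis". Section 9.4, in defining the per-protocol set, says "missing data will be seen as a protocol violation" and gives exclusion from that set as the consequence.

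**The concern.** In a drug trial, discontinuing a patient after a violation can mean stopping the study drug, and outcome collection may go on. Here nothing is given, so leaving the study means only that outcomes stop being recorded. A clause that protects patients elsewhere has no such function in this cohort and costs endpoint data.

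The decision is also open. Patients are assigned to the controlled or uncontrolled group at Visit 0 (section 4.4.2), there is no blinding, and no text withholds group or events from the sponsor or investigator. The length of follow-up behind the main comparison could then depend on case-by-case judgements made with that knowledge. Keeping such patients in the intention-to-treat set does not restore the events that were never collected.

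**Working it through.** **Step 1. The clauses side by side**

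| Section | What it provides | Effect here |
|---|---|---|
| 11.1.2 | Sponsor may discontinue, or permit to continue, after a significant deviation | Discretionary end of participation |
| 6.2 | Investigator may withdraw for deviations; data up to withdrawal plus a final evaluation | No later outcomes described |
| Summary, 5 | Non-interventional, usual care, contact at visits only | No treatment to stop; no other study contact with the patient |
| 9.1 | All entered patients in the intention-to-treat analysis | Patient stays in the set without further events |
| 9.4 | Missing data a violation, for per-protocol membership | Shares a term with 11.1.2 |

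The first four rows together give the point: 11.1.2 and 6.2 permit a loss of primary-endpoint data that the intent of 9.1 argues against.

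**Step 2. Can a size be given?** The plan has no figure for discontinuation after violations; the 15% drop-out in section 4.5 is not split by reason. An illustration shows what a size would depend on.

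Inputs from section 4.5: 1.2 events per person-year, and 0.72 in controlled patients, ratio 0.72/1.2 = 0.60. The protocol gives 1.2 as the rate in an entire cohort, so using it for the uncontrolled group is an assumption. Also assumed: a fraction f of uncontrolled patients is discontinued halfway, these patients have m times the rate of the other uncontrolled patients, and no controlled patient is discontinued.

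- Rate in the other uncontrolled patients: r0 = 1.2/(1 − f + f·m).
- Pooled observed rate: [(1 − f)·r0 + 0.5·f·m·r0]/(1 − 0.5·f).

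| f | m | r0 | Pooled uncontrolled rate | 0.72 / pooled rate |
|---|---|---|---|---|
| 0.05 | 1.5 | 1.171 | 1.186 | 0.61 |
| 0.10 | 2 | 1.091 | 1.148 | 0.63 |
| 0.20 | 3 | 0.857 | 1.048 | 0.69 |

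Now take instead the mean of each patient's own annualised rate. Its expectation is (1 − f)·r0 + f·m·r0 = r0·(1 − f + f·m) = 1.2, whatever f and m are, and the ratio stays at 0.60. The same discontinuations bias one estimator and leave the other's mean unchanged.

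**Step 3. Does more discontinuation in one group suffice?** A simulation used rates 0.72 and 1.2, 18 months from Visit 0 to Visit 3 (21 − 3), and an assumed gamma-distributed patient risk with variance 1. Yearly discontinuation hazards (controlled / uncontrolled) are assumptions.

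| Hazards | Linked to individual risk? | Pooled ratio | Ratio of mean per-patient rates |
|---|---|---|---|
| 0.10 / 0.10 | No | 0.600 | 0.719/1.201 = 0.599 |
| 0.05 / 0.20 | No | 0.599 | 0.719/1.199 = 0.600 |
| 0.05 / 0.20 | Yes | 0.657 | 0.717/1.193 = 0.601 |
| 0.10 / 0.30 | Yes | 0.670 | 0.722/1.190 = 0.607 |

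Small departures from 0.600 in the unlinked rows and in the last column are simulation noise. Fourfold more discontinuation in the uncontrolled group does not by itself move the ratio. Bias towards no difference needs discontinuation that follows event risk within a group, and then appears in the pooled ratio.

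**Step 4. The planned analyses.** Section 9.3.3 compares the composite with a Mann-Whitney test, which needs one value per patient and ranks rather than averages them, so neither calculation above maps directly onto it. The same section analyses presence or absence of the composite in year 1 by logistic regression. There, a patient discontinued event-free before the year ends has an outcome that is only partly observed.

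**The case against.** The strongest defence is that 11.1.2 is standard text, limited to significant deviations, with continuation as an express option and a sensible criterion. A sponsor applying it would have little reason to remove a patient from a cohort over a minor lapse. This stands, and it limits how often the clause would bite. It does not supply any follow-up for those who are removed.

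Three stronger readings are tempting and are not supported.

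- *A reader might infer that a missed visit or form is enough to trigger discontinuation.* Section 9.4 uses the violation label only to define the per-protocol set, with exclusion from that set as the consequence, and it goes on to provide for imputation in the intention-to-treat set. Section 11.1.2 does not name missing data. It does list non-adherence to criteria for the primary objective's variables, and it shares the term, so the link should be ruled out in the text; no passage makes it.
- *A reader might infer that the rule selectively censors sicker patients.* Section 11.1.2 mentions neither severity, control status nor events. The inference needs sicker patients to commit more significant violations and the sponsor then to choose discontinuation. Both are possible; neither is documented. The outcome-linked discontinuation that the protocol does state, for hospitalised exacerbations in section 8.1, is a separate matter.
- *A reader might take the shift from 0.60 to 0.61–0.69 as what the plan would report.* It follows from assumed inputs and a pooled estimator that the protocol does not specify.

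**Conclusion.** The concern holds as a design and wording fault. The violation and withdrawal clauses carry drug-trial text into a non-interventional cohort and permit primary-endpoint follow-up to be ended by a discretionary decision that is open to knowledge of control status and events. That conflicts with the intent of section 9.1 and can leave year-1 outcomes incomplete. It may bias the comparison if discontinuation tracks event risk. The documents do not establish that it does, and the size depends on the discontinuation pattern and on how the rate is estimated, so no magnitude should be presented as a consequence of the plan. The conclusion rests on one reading: because 6.2 asks only for data up to withdrawal plus a final evaluation, and section 5 rules out contact between visits, nothing is collected afterwards. The fault is worth correcting because it is avoidable and cheap to remove.

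**What to change.** - In 11.1.2, and consistently in 6.2, state that a protocol violation or deviation is recorded and may affect per-protocol membership, but does not by itself end data collection. Primary-endpoint data are collected to Visit 3 unless the patient withdraws consent.
- Delete the examples on study-drug compliance and prohibited medication from 11.1.2.
- In 9.4, limit the missing-data statement to per-protocol membership and say that it does not lead to discontinuation.

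The cost is a protocol wording amendment and continued visits for the patients concerned. The downside is that data from patients with deviations stay in the intention-to-treat set, which is what section 9.1 already intends.
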